9.2.1. Research Electronic Data Capture (REDCap)	
9.2.2. Paper source data	5
9.2.3. Handwritten entries	6
9.3. DATA MANAGEMENT	6
9.4. RECORDS RETENTION	6
10. STUDY MONITORING, AUDITING, AND INSPECTING 2	6
10.1. DATA AND SAFETY MONITORING PLAN (DSMP)	6
10.2. Auditing and Inspecting 2	7
11. ETHICAL CONSIDERATIONS 2	7
12. STUDY FINANCES	7
12.1. Funding Source	7
12.2. CONFLICT OF INTEREST	7
12.3. Subject Stipends or Payments	7
13. PUBLICATION PLAN	8
14. REFERENCES	8

List of Abbreviations

AD – Alzheimer's disease MCI – Mild Cognitive Impairment CSF – Cerebrospinal Fluid RAPA – Sirolimus (Rapamune®) S6K1-P - Ribosomal protein S6 Kinase Beta-1 HPLC/MS/MS – High Performance Liquid Chromatography-Mass Spectrometry MMSE– Mini Mental State Examination (MMSE) MoCA - Montreal Cognitive Assessment CDR – Clinical Dementia Rating MINT - Multilingual Naming Test HVLT-R – Hopkins Verbal Learning Test-Revised CVLT-III – California Verbal Learning Test III NPI – Neuropsychiatric Inventory FAQ – Functional Activities Questionnaire GDS – Geriatric Depression Scale

Study Summary

Title	Cognition, Age, and RaPamycin Effectiveness – DownregulatIon of thE mTor pathway (CARPE DIEM)
Protocol Number	20190850Н
Phase	2
Methodology	Open label
Study Duration	Between 12-18 weeks
Study Center(s)	UTHSA McDermott (Biggs, RII)
Objective	To evaluate central nervous system penetration of orally administered RAPA in older adults with Mild Cognitive Impairment (MCI) or early Alzheimer's disease (AD) and investigate associated safety, tolerability, target engagement, cognition, and functional status as initial proof-of-concept for a larger phase 2 clinical trial
Number of Subjects	Screen up to 60 with intent for 10 completers. Additional subjects may be enrolled if attrition exceeds the anticipated rate (~25%).
Inclusion Criteria	 Both genders and all ethnic groups Ages 55 to 85 years Diagnosis of MCI or AD with a Clinical Dementia Rating Scale (CDR) score = 0.5 – t Labs: Normal blood cell counts without clinically significant excursions; normal liver and renal function; and glucose control (HbA1c < 6.5%). Lipid panel and PT/PTT/INR within normal limits A Legally Authorized Representative (LAR) designated to sign informed consent (if necessary) for Visit 1 An available LAR or other study partner for reported outcomes must accompany participants to all study visits. Participants must have no travel plans over the three to four months following enrollment that would interfere with scheduling visits following consent Stable dose of AD medications (Donepezil, rivastigmine, Memantine, galantamine) for at least three months prior to baseline (visit 2) is allowed

Exclusion Criteria	 Diabetes (HBA1c≥6.5% or antidiabetic medications) History of skin ulcers or poor wound healing Current tobacco or illicit drug use or alcohol abuse Use of anti-platelet or anti-coagulant medications other than aspirin Current medications that affect cytochrome P450 3A4 (see section 4.3); current or recent medications for hypertriglyceridemia (eg, Gemfibrozil) Hypersensitivity or history of allergy to Rapamycin Immunosuppressant therapy within the last year; current treatment with hydroxychloroquine and chloroquine (requires "washout period" of 14 days) Chemotherapy or radiation treatment within the last year Current or chronic history of liver disease or known hepatic or biliary abnormalities History of primary hypertriglyceridemia. Abnormal triglycerides >200 or LDL cholesterol >193, or other abnormal labs deemed clinically significant upon investigator review Current or chronic history of pulmonary disease or abnormal pulse oximetry (<90%) Chronic heart failure Pregnancy Recent history (past six months) of myocardial infarction, active coronary artery disease, intestinal disorders, stroke, or transient ischemic attack Significant neurological conditions other than AD Poorly controlled blood pressure (systolic BP>160, diastolic BP>90 mmHG - two readings) Active inflammatory, COVID-19, autoimmune, infectious, hepatic, gastrointestinal, malignant, and/or psychiatric disease History of, or MRI, or CT positive for, any space occupying lesion, including mass effect or abnormal intracranial pressure, which would indicate contraindications to lumbar puncture Organ transplant recipients
Study Product, Dose, Route, Regimen	RAPA (Sirolimus, Rapamune®) will be administered orally as (1) 1mg capsule daily
Duration of administration	RAPA will be administered once daily for 8 consecutive weeks.
Statistical Methodology	Similar to an early phase 2 trial, we are seeking preliminary evidence of the degree of central nervous system penetration of orally administered RAPA in older adults with MCI and early AD and investigate associated safety, tolerability, target engagement, cognition, and functional status as initial proof-of-concept for a larger phase 2 clinical trial. We will report the change in post intervention laboratory values relative to baseline with the 95% confidence interval. Experimental results will be expressed as means \pm SE.

1. Introduction

This document is a protocol for a human research study. This study will be conducted according to Good Clinical Practice guidelines as adopted by FDA, applicable government regulations, and within Institutional research policies and procedures.

1.1. Background

The mechanistic (formerly mammalian) target of rapamycin (mTOR) signaling pathway is crucial for cell metabolism and its dysregulation contributes to age-related chronic medical conditions. RAPA (rapamycin, sirolimus), an FDA-approved immunosuppressant, effectively inhibits the mTOR pathway and thus manifests a wide variety of effects. In preclinical trials, orally administered RAPA extends longevity and mitigates the development of chronic diseases^{1,2}. Moreover, growing research suggests that RAPA can alter the cellular and biological processes underlying the development of Alzheimer's disease (AD), including abnormal protein accumulation, diminished autophagy, and attenuated cerebral blood flow³⁻⁶. Specifically, the mTOR pathway exerts a strong influence on amyloid beta ($\alpha\beta$) and tau deposition consistent with upregulated mTOR signaling as observed in postmortem brain tissue from individuals with AD⁷. In multiple mouse models, orally administered RAPA dampens mTOR signaling, reduces cerebral $\alpha\beta$ levels by approximately 40-50%, and diminishes tau aggregation^{5,6}, remediating cognitive deficits⁴. Suppression of the mTOR gene similarly diminishes a deposition⁸, directly implicating mTOR inhibition as the mechanism mediating RAPA's effect on neuropathological protein accumulation. In addition to exerting direct influence on a and tau accumulation, mTOR activity has been shown to accelerate abnormal protein accumulation by suppressing autophagy^{5,6}. In contrast, RAPA-treated mice with pharmacologically increased autophagy demonstrate a three-fold increase in lysosomal aß levels⁹, implicating the drug's ability to upregulate autophagy in neuropathological protein clearance.

RAPA has also been shown to restore cerebrovascular function⁴, which evidences early alterations in AD including chronic reductions in cerebral perfusion¹⁰, impaired endothelium-dependent vasodilation¹¹, and increased blood-brain barrier permeability¹². RAPA increases nitric oxide production through the phosphorylation of endothelial nitric oxide synthase, inducing cortical vasodilation⁴. In mice, RAPA treatment restored cerebral blood flow levels and increased cerebral blood vessel density⁴. These changes were coupled with diminished aβ deposition in the blood vessels, reduced aβ plaques, and lower incidence of cerebral microbleeds⁴. Finally, RAPA dramatically dampened microglial activation,³ a hallmark pathological feature of AD¹³. Activated microglial cells release pro-inflammatory cytokines and reactive oxygen species¹⁴, inducing neuronal damage. In transgenic AD mouse models, RAPA diminished microglial activation, subsequently reducing interleukin 1-β, enhancing N-methyl-D-aspartate (NDMA) activity, and facilitating memory³.

1.2. Innovation

Treatment with RAPA to measure the concentration of the drug that reaches the cerebrospinal fluid and crosses the blood-brain barrier is a novel approach to help identify targeted therapy for MCI and Alzheimer's disease.

1.3. Preliminary data

While human clinical trials of RAPA in AD have not yet been conducted, trials for other conditions have provided preliminary support for the cognitive benefits of RAPA treatment. In a sample of heart transplant recipients, four-week RAPA treatment (everolimus) improved performance on measures of memory, attention, and executive function, as well as enhanced mood¹⁵. To evaluate safety and tolerability in older adults, we recently conducted a randomized, placebo-controlled trial of eight-week RAPA treatment (1 mg/day) in individuals ages 70-95 years old¹⁶. No serious adverse events occurred. The reported adverse events were limited to facial rash (N=1), stomatitis (N=2, 1 placebo and 1 RAPA treated), and gastrointestinal distress

	PLACEE	BO (n=14)		RAPA (n=11)				Group Difference		
	Pre	Post	P value	Difference (95% CI)	Pre	Post	P value	Difference (95% CI)	P value	Differenc e (95% CI)
HgB	13.81± 1.53	13.98± 1.63	0.33	0.16 [-0.19, 0.51]	13.94 ± 1.35	13.12 ± 1.22	0.003	-0.82 [-1.29, -0.35]	0.001	0.98 [0.43, 1.54]
НСТ	41.29 ± 4.13	41.96 ± 4.54	0.21	0.67 [-0.42, 1.76]	41.57 ± 3.79	39.24 ± 3.75	0.002	-2.34 [-3.57, -1.1]	<0.001	3.01 [1.45, 4.56]

(N=2). Statistically, but not clinically significant, decrements were observed in multiple erythrocyte parameters (i.e. hemoglobin, hematocrit, red blood cell count).

HgB=hemoglobin HCT=hematocrit

¹⁶ Ellen Kraig, et al. Table 4

Measures of cognition and physical functioning were unchanged, although several informants reported anecdotal observations of improved cognition. A subset of individuals underwent assessment of cutaneous vasodilation, a measure of nitric oxide-dependent endothelial function, and displayed a strong trend towards post-treatment improvement (p=0.052). In light of the compelling preclinical data demonstrating that RAPA restores cognition in AD by exerting influence on multiple pathophysiological pathways^{4-6,9}, coupled with data on safety and possible cognitive benefits derived from human trials, we are now well-positioned to conduct the first clinical trial of RAPA in individuals with symptomatic MCI and AD.

1.4. Dose Rationale and Risk/Benefits

Eligible participants will be treated with 1 mg of RAPA daily for 8 consecutive weeks. The most common adverse events include mucositis, stomatitis, diarrhea, nausea, and acneiform rash. Pneumonitis, the most serious potential adverse event, occurs in \leq 1-5% of cases, typically after prolonged drug exposure (\geq six months). In our recent clinical trial of elderly adults receiving 1mg RAPA daily, the same dosage to be used in this proposal, no serious adverse events occurred¹⁶. The reported adverse events were limited to facial rash (N=1), stomatitis (N=1; 1 on placebo and 1 on RAPA), and gastrointestinal distress (N=2).

The study will consist of a screening/baseline period of up to 30 days pre-study drug, with a 56-day (\pm 3 day) treatment period, and a post-intervention visit for study outcomes on final day of dosing and up to +14 days. The study duration is not expected to exceed 18 weeks for participants.

2. Study Objective

The objective of the study is to assess the degree of central nervous system penetration of orally administered RAPA treatment using collecting cerebral spinal fluid (CSF), and begin collecting initial data on safety, tolerability, target engagement, AD-related markers, and AD-relevant outcomes for future trials.

3. Study Design

3.1. General Design

This study is an open-label pilot study of orally administered RAPA to measure its target engagement in CSF and blood, and to establish the feasibility and safety of RAPA treatment in older adults with MCI and early stage AD as initial proof-of-concept for a larger Phase 2 clinical trial.

Aim 1: To assess the degree of central nervous system penetration and drug clearance with 8-week RAPA treatment. Lumbar punctures will be performed before treatment and after the final RAPA dose 8 weeks later to assess CSF levels of the drug. Quantification will be completed with HPLC/MS/MS chromatography.

Aim 2: To assess the safety and tolerability of 8-week RAPA treatment in older adults with MCI and AD. At three timepoints across the 8-week intervention, safety evaluations will be conducted including monitoring for adverse events, study compliance, vital signs, and laboratory assessment (CBC, comprehensive metabolic panel (CMP)

Aim 3: To investigate target engagement of RAPA treatment for AD pathology. We will evaluate levels of relevant AD biomarkers (e.g., total tau, phosphorylated tau, Aβ40 and Aβ42, neurofilament light, and glial fibrillary acidic protein), inflammatory (e.g., IL-6, PAI-1, soluble ICAM-1) and other relevant analytes in the CSF and/or blood at time points prior to RAPA treatment and after 8 weeks on the drug.

Aim 4: To evaluate changes from baseline in cognition, functional status, and physical functioning after 8 weeks of RAPA treatment. Pre- and post-treatment changes in cognition, disease severity, functional status, mood, and physical functioning will be assessed using a battery of tests appropriate for use with AD populations.

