3.2. Study Endpoints

a) **Primary outcome: To determine blood brain barrier penetrance of RAPA in older adults with mild cognitive impairment or early symptomatic Alzheimer's disease.** Lumbar punctures will be performed at baseline and after the final RAPA dose, to assess CSF levels of the drug. Quantification will be completed with HPLC/MS/MS chromatography.

Secondary outcomes:

- b) To assess the safety and tolerability of 8-week RAPA treatment in older adults with AD. At three timepoints across the 8-week intervention, safety evaluations will be conducted including monitoring for adverse events, study compliance, vital signs, and laboratory assessment (CBC, comprehensive metabolic panel (CMP), blood RAPA levels).
- c) **To investigate target engagement of RAPA treatment in AD.** We will evaluate levels of relevant AD biomarkers (e.g., total tau, phosphorylated tau, Aβ40 and Aβ42, neurofilament light, and glial fibrillary acidic protein), inflammatory (e.g., IL-6, PAI-1, soluble ICAM-1) and other relevant analytes in the CSF and/or blood at time points prior to RAPA treatment and after 8 weeks on the drug.
- d) To evaluate changes from baseline in cognition, functional status, and physical functioning after 8 weeks of RAPA treatment Pre-intervention to post-intervention change in cognitive tests (MoCA, HVLT-R, Craft Stories, Benson Figure Copy and Delayed Recall, Trail Making Test Parts A&B, Number Span Test, Semantic Fluency, Phonemic Fluency, MINT, Hayling), physical functioning assessment (electronic gait mapping under single and dual-task conditions, grip strength), and questionnaires/semi-structured interviews (CDR, GDS, NPI, FAQ,).

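### Do Aim 3 and outcome (c) need rewriting because they report AD and inflammatory markers as target engagement and give S6K1-P no role?

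*Combined protocol and SAP*

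**What the plan says.** Section 2 gives the aims beyond CNS penetration as a list: to "begin collecting initial data on safety, tolerability, target engagement, AD-related markers, and AD-relevant outcomes for future trials". Target engagement and AD-related markers are two entries in it.

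Aim 3 in section 3.1 brings them together: "To investigate target engagement of RAPA treatment for AD pathology. We will evaluate levels of relevant AD biomarkers". Outcome (c) in section 3.2 opens "To investigate target engagement of RAPA treatment in AD". It then names the same AD and inflammatory examples and closes with an open category, "and other relevant analytes in the CSF and/or blood at time points prior to RAPA treatment and after 8 weeks on the drug".

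The Study Summary uses the shorter form. Its objective is to "investigate associated safety, tolerability, target engagement, cognition, and functional status as initial proof-of-concept for a larger phase 2 clinical trial", with no separate entry for AD markers. The trial title refers to "DownregulatIon of thE mTor pathway".

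The abbreviation list has "S6K1-P - Ribosomal protein S6 Kinase Beta-1". Section 6.2 gives RAPA and S6K1-P levels as the first stated use of the 60 mL research blood draw, ahead of the AD and inflammatory markers. Section 6.7 repeats the research labs at Visit 7 by reference back to Visit 2.

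On analysis, the Study Summary says "We will report the change in post intervention laboratory values relative to baseline with the 95% confidence interval", and section 7.2 says the same in general terms.

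**The concern.** The drug's target, by the protocol's own account, is mTOR: the title names that pathway and section 5.1 identifies mTOR as the kinase inhibited. A reader would expect the engagement outcome to name a measure of mTOR activity. Instead it names tau, amyloid, neurofilament light, GFAP and three inflammatory proteins. Section 2 appears to treat the AD markers among these as something different.

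S6K1-P makes the gap more visible. Blood is drawn for it, but no aim, outcome, assay description or statistical text says what it is for. If it is the engagement measure, the plan does not say so; if it is not, its purpose is unexplained.

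The stake would be interpretive. In an open-label study with an open analyte category, the result that carries the engagement heading could be chosen after the data are seen. A change in tau could then be presented to the planners of the larger trial as evidence that the drug reached its target, or a flat result as evidence that it did not.

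**Working it through.** There is no figure in the plan to reproduce and no sampling calculation that bears on the point. The check is a comparison of texts with a few counts.

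**1. Is the observation correct?** Yes. Outcome (c) names total tau, phosphorylated tau, Aβ40, Aβ42, neurofilament light and GFAP (6), and IL-6, PAI-1 and soluble ICAM-1 (3), so 6 + 3 = 9. None is identified as a measure of mTOR. S6K1-P is named in two places only, the abbreviation list and the Visit 2 blood draw. That is 0 of 4 aims and 0 of 4 outcomes.

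**2. Does section 2 contradict outcome (c)?** Set the five section 2 items against the three secondary outcomes in section 3.2:

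| Section 2 item | Outcome in 3.2 |
|---|---|
| safety | (b) |
| tolerability | (b) |
| target engagement | (c) |
| AD-related markers | (c) |
| AD-relevant outcomes | (d) |

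The five items fall 2 + 2 + 1. Safety and tolerability are merged in (b) in the same way that engagement and AD markers are merged in (c), and nobody would call the first a contradiction. An introductory list does not promise one outcome per entry.

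**3. Do the documents define engagement as a direct mTOR measurement?** No. Aim 3 limits the term to AD pathology. The opening of section 3.1 uses it broadly, for what will be measured in CSF and blood, before any aim is stated. The Study Summary objective fits the merged reading. Section 1.1 supplies the link. It reports less amyloid and less tau aggregation alongside dampened mTOR signaling in mice, notes that suppressing the mTOR gene similarly lowers deposition, and concludes that mTOR inhibition is the mechanism behind the effect on these proteins. Using the protein markers as a downstream readout is therefore the protocol's own logic.

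**4. Is S6K1-P left without an analysis?** It need not be. The examples in (c) are illustrative and end in an open category. The draw is planned before treatment and, by cross-reference, at Visit 7. In the Study Summary, the sentence promising change from baseline with a 95% confidence interval directly follows one that lists target engagement among the things to be investigated, so it is not confined to safety laboratory tests.

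**5. How telling are the other silences?** Not very.
- The CSF list at Visit 2 omits S6K1-P, but S6K1-P is listed under the blood draw.
- The chromatography item in the section 6.2 assay text names no analyte, not even RAPA.
- The blood volumes, 40 + 2 + 18 = 60 mL, are matched to no analyte at all.

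**6. What would differ under tighter wording?** The primary outcome (CSF RAPA) would not. Nor would the visits, the samples, the pre/post estimates or their intervals. The plan attaches no threshold or success criterion to engagement, and the sample size rests on feasibility (section 7.1). Only the heading over a set of results would move.

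**The case for a change.** The best case for a change is that target engagement is prominent in this protocol. It is in the first sentence of section 3.1, in the Study Summary objective and in the Study Summary's statistical paragraph, as groundwork for a larger trial. A pilot should say which measurement answers a question it raises so often. That an open category might cover S6K1-P is not the same as designating it. Clearer wording would also cost very little.

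Part of this stands. The documents do not say what S6K1-P measures or which assay will be used, and a reader cannot be sure that it is the intended engagement measure. A one-line statement would have been tidier. It is also true that a marker change labelled only as engagement would tell the planners of the next trial less than the same change reported under the analyte's name.

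What does not stand is the step from an unspecified label to a defect in the plan. Choosing an analyte after the fact gains little where no claim of success, stopping decision or go/no-go rule rests on it, and where the intended result for each laboratory value is a change with an interval. A requirement that engagement be shown by a direct mTOR measure is a preference about terminology that these documents neither state nor contradict.

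**Conclusion.** No change is needed. This is missing detail and loose labelling in a pilot intended for about 10 completers, and analysts can fill it sensibly: report the Visit 2 to Visit 7 change in S6K1-P with its 95% confidence interval beside the AD and inflammatory markers, each under its own name, and describe the latter as downstream markers. The effect on the primary outcome and on every planned estimate is nil. The effect on interpretation is confined to the words used over outcome (c).

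The conclusion rests on three assumptions: that the Visit 7 cross-reference does repeat the full Visit 2 research draw, that all analytes measured are reported and not a chosen few, and that no decision rule for the larger trial is later tied to an engagement result from this study. If the last failed, the engagement measure would need to be named in advance.

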3.2. Study Endpoints

a) **Primary outcome: To determine blood brain barrier penetrance of RAPA in older adults with mild cognitive impairment or early symptomatic Alzheimer's disease.** Lumbar punctures will be performed at baseline and after the final RAPA dose, to assess CSF levels of the drug. Quantification will be completed with HPLC/MS/MS chromatography.

Secondary outcomes:

- b) To assess the safety and tolerability of 8-week RAPA treatment in older adults with AD. At three timepoints across the 8-week intervention, safety evaluations will be conducted including monitoring for adverse events, study compliance, vital signs, and laboratory assessment (CBC, comprehensive metabolic panel (CMP), blood RAPA levels).
- c) **To investigate target engagement of RAPA treatment in AD.** We will evaluate levels of relevant AD biomarkers (e.g., total tau, phosphorylated tau, Aβ40 and Aβ42, neurofilament light, and glial fibrillary acidic protein), inflammatory (e.g., IL-6, PAI-1, soluble ICAM-1) and other relevant analytes in the CSF and/or blood at time points prior to RAPA treatment and after 8 weeks on the drug.
- d) To evaluate changes from baseline in cognition, functional status, and physical functioning after 8 weeks of RAPA treatment Pre-intervention to post-intervention change in cognitive tests (MoCA, HVLT-R, Craft Stories, Benson Figure Copy and Delayed Recall, Trail Making Test Parts A&B, Number Span Test, Semantic Fluency, Phonemic Fluency, MINT, Hayling), physical functioning assessment (electronic gait mapping under single and dual-task conditions, grip strength), and questionnaires/semi-structured interviews (CDR, GDS, NPI, FAQ,).

